#### **8.3.2. Long-Term Follow-up**

Once subjects have cGVHD progression, or have progression of their underlying malignancy (for subjects who have not withdrawn consent), they will be contacted approximately every 12 weeks ( $\pm 14$  days) by clinic visit or telephone to assess survival and the use of alternative cGVHD therapy. In addition, subjects who have progressive cGVHD will continue to have the Lee Symptom Scale and SF-36 assessments until the week 60 visit. Subjects will be contacted until death, subject withdrawal, lost to follow-up, or study termination by the Sponsor, whichever occurs first.

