### **Patient Reported Outcomes**

SF-36 summary scores will be evaluated; detailed analyses will be covered in the statistical analysis plan (SAP).

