1.6. Testing Procedure and Level of Significance in the primary analysis

To preserve the study wise type I error rate of 0.05, the primary and secondary endpoints will be tested based on a serial gatekeeping testing procedure at the two-sided significance level of 0.05 according to the hierarchical order specified below:

1. Response rate at 48 weeks
2. Time to withdrawal of all corticosteroids for treatment of cGVHD
3. Time to withdrawal of all ISTs, including corticosteroids for treatment of cGVHD (with the exception of ibrutinib/placebo)
4. Response rate at 24 weeks
5. Improvement in Lee cGVHD Symptom Scale at 2 consecutive visits
6. Proportion of subjects who achieve reduction of corticosteroids dose level to less than 0.15 mg/kg/d at 24 weeks sustained for at least 30 days

Since the number of deaths at the primary analysis is expected to be low, formal analysis for OS will be performed at the final analysis. However, summary of OS will be provided based on available data at the time of the primary analysis. Duration of response will be analyzed to support the response endpoints.

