Improvement in overall score on Lee cGVHD Symptom Scale	
Proportion of subjects who had Lee total score decreasing at least 7 points at 2 consecutive visits with no PD, relapse of underlying disease or start of subsequent cGVHD treatment.
 
Proportion of subjects who had Lee total score decreasing at least 7 points at any time during the study (not preceded by PD, relapse of underlying disease or start of subsequent cGVHD treatment)
	
Comparison of the proportions between the two arms will be performed using chi-square test.
 
Supportive: Summary of the proportions of subjects with at least 7 points improvement at any
	ITT

Endpoint	Definition	Analysis Method	Population
	Mean Lee scores overtime	time will be provided. Summary of mean Lee scores overtime and graphs by treatment arm will be provided	
Proportion of subjects who achieve reduction of corticosteroids dose level to less than 0.15 mg/kg/d at 24 weeks sustained for at least 30 days	Proportion of subjects with prednisone equivalent dose reduction to a level of less than 0.15 mg/kg/d for a duration of at least 30 days at 24 weeks Mean daily corticosteroid dosing overtime	Comparison of the proportions between the two arms will be performed using Chi-square test Supportive: Mean (95%CI) of daily corticosteroid dosing over time will be summarized and plotted by arm	ITT
Duration of response	The interval between the date of initial documentation of a response (PR or better), and the date of first documented evidence of progressive cGVHD, relapse of underlying disease, start of subsequent cGVHD treatment, or death for responders only.	DOR will be estimated by Kaplan-Meier methodology: median DOR and landmark estimates with 2-sided 95% CIs will be provided for each treatment arm. K-M plots will be provided	Responders include subjects with response at any time during study treatment
Overall Survival	Time from the date of randomization until the date of death due to any cause. All deaths observed at the time of the data extraction date will be considered as events. For subjects who were not known to have died at the time of the analysis, OS data will be censored at date last known alive.	Survival will be estimated by Kaplan-Meier methodology: median OS and landmark estimates with 2-sided 95% CIs will be provided for each treatment arm. Kaplan-Meier plots will be provided	ITT
Exploratory Endpoints			

Endpoint	Definition	Analysis Method	Population

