Improvement in SF-36 patient reported outcome	SF-36 subscales over time for each treatment arm	Descriptive summary statistics mean and 95% CI for each timepoint	ITT
Improvement in Karnofsky performance scale score	Karnofsky scores over time for each treatment arm	Descriptive summary statistics mean and 95% CI for each timepoint	ITT

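### The exploratory SF-36 scores and the supportive mean Lee scores are planned only as raw visit means by arm, so neither change from baseline nor an arm difference is estimated for them

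*SAP*

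**What the plan says.** **SF-36.** SAP Section 4, Table 2, names an exploratory endpoint of improvement in SF-36. It defines the endpoint as "SF-36 subscales over time for each treatment arm" and analyses it by "Descriptive summary statistics mean and 95% CI for each timepoint". The Karnofsky row uses the same method wording. Protocol Section 10.4.3 had left the detail to the SAP: "SF-36 summary scores will be evaluated; detailed analyses will be covered in the statistical analysis plan (SAP". The protocol therefore speaks of summary scores and the SAP of subscales. SAP Section 6, which lists changes from the protocol, does not mention the difference.

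**Lee, tested endpoint.** Step 5 of the hierarchy in SAP Section 1.6 is "Improvement in Lee cGVHD Symptom Scale at 2 consecutive visits". Table 2 defines it as "Proportion of subjects who had Lee total score decreasing at least 7 points at 2 consecutive visits with no PD", also free of relapse and of new cGVHD treatment. On the arms it says "Comparison of the proportions between the two arms will be performed using chi-square test".

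**Lee, supportive.** Under the same row: "Summary of mean Lee scores overtime and graphs by treatment arm will be provided".

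**Collection.** Both questionnaires are completed at screening or before the first dose (Protocol 8.1.1 and 8.2.1.1) and at each cGVHD activity assessment (7.3.2). They continue in response follow-up after study drug stops for reasons other than progression (8.3.1). In long-term follow-up, "subjects who have progressive cGVHD will continue to have the Lee Symptom Scale and SF-36 assessments until the week 60 visit". The SAP states no rule for missing questionnaires.

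**The concern.** An endpoint called improvement should measure change, and a randomised trial should report the difference between its arms. The SF-36 means and the supportive Lee means do neither. The reader gets two series of means and must judge the difference by eye. Any chance imbalance at baseline stays in those means, and the information in each subject's own baseline goes unused.

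The step-5 Lee endpoint is dichotomised, so these means are the only planned use of either questionnaire on its continuous scale. They are also the only planned place for questionnaires completed after cGVHD progression, because the responder definition excludes improvement after progression.

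At stake are the clarity and precision of the patient-reported evidence. The primary result is not.

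**Working it through.** **1. The plan's own figure.** The SAP gives no precision or power for Lee or SF-36. Its only sample-size figure is 186, for response of 30% against 50%, two-sided 5%, 80% power (SAP 1.4). With pooled variance and no continuity correction:

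n per arm = [1.960 × √(2 × 0.4 × 0.6) + 0.842 × √(0.3 × 0.7 + 0.5 × 0.5)]² / 0.20² = 93.

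The total is 186 and the power at 93 per arm is 0.800, so the figure reproduces.

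**2. Inputs for the scores.** The 193 subjects randomised 1:1 (SAP 1.1) give about 96.5 per arm. The documents state neither the SD nor the baseline-to-visit correlation r. Results are therefore in SD units, with r assumed between 0.3 and 0.8.

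**3. What the planned intervals show.** Each arm mean has half-width 1.96 / √96.5 = 0.200 SD. Two such intervals stop overlapping only when the means differ by 2 × 1.96 / √96.5 = 0.399 SD. The interval for the difference itself has half-width 1.96 × √(2 / 96.5) = 0.282 SD. Judging by overlap is therefore stricter than the direct contrast, even before any adjustment.

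**4. Effect of using baseline.** Adjusted half-width = 0.282 × √(1 − r²). Unadjusted change-score half-width = 0.282 × √(2(1 − r)), if the SD is equal at both times. The last column is the power to detect an illustrative 0.3 SD difference; without adjustment it is 0.549.

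| r (assumed) | Raw | Change only | Baseline-adjusted | Narrower than raw | Adjusted power, 0.3 SD |
|---|---|---|---|---|---|
| 0.3 | 0.282 | 0.334 | 0.269 | 5% | 0.589 |
| 0.5 | 0.282 | 0.282 | 0.244 | 13% | 0.672 |
| 0.6 | 0.282 | 0.252 | 0.226 | 20% | 0.740 |
| 0.7 | 0.282 | 0.219 | 0.202 | 29% | 0.831 |
| 0.8 | 0.282 | 0.178 | 0.169 | 40% | 0.935 |

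The gain comes from baseline as a covariate. Change scores alone are less precise than raw scores when r is below 0.5.

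**5. Fewer forms.** With 70 per arm the half-width falls from 0.331 to between 0.316 and 0.199 SD. With 50 per arm it falls from 0.392 to between 0.374 and 0.235 SD. The proportional gain is the same.

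**6. Who contributes.** Up to Week 60, subjects with cGVHD progression are still scheduled to complete both questionnaires, so Weeks 25 and 49 are covered. After Week 60 they stop while others continue, so later means leave them out by schedule. For relapse of the underlying malignancy, response follow-up ends (8.3.1) and the continuation in 8.3.2 names only progressive cGVHD. Death, withdrawal and skipped forms also remove scores.

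**The case against.** The strongest reply is that these analyses are exploratory or labelled supportive and sit outside the hierarchy, and that descriptive reporting is a legitimate choice for them. That stands as a limit on importance. It does not explain why an endpoint labelled improvement omits change, or why an arm difference is left out when the data are in hand.

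A reader might infer that Lee improvement is never estimated or compared. The documents do not support that. The step-5 test is a within-subject fall of at least 7 points (read here as from baseline, since the row names no reference visit), compared between arms in the ITT population.

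A reader might also infer that the visit means describe only subjects who are doing well. That goes too far at Weeks 25 and 49, because collection continues after drug discontinuation and after cGVHD progression. What remains is loss through death, relapse, withdrawal and missing forms. The documents give no size for it.

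The proposed model has gaps of its own. It assumes data are missing at random and does not resolve death. Post-progression contacts are roughly every 12 weeks, ±14 days, by clinic visit or telephone, so they need visit windows. These points stand and are carried into the fix.

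**Conclusion.** The point holds for the SF-36 scores and the supportive mean Lee scores, and only for those. For them the plan estimates neither change nor an arm difference and leaves the baseline unused. It is a minor but real improvement to the plan: no gated result and no alpha is involved.

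The size depends on a correlation that the documents do not give. For r from 0.3 to 0.8, with all 193 subjects contributing, the interval for an arm difference is 5% to 40% narrower. No single value in that range can be presented as the trial's actual loss, and the comparison is with an unadjusted difference that the SAP does not itself plan to report.

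A reader might also take the baseline as free of steroids for everyone. It is not. Protocol 4.2 admits subjects who received corticosteroids for cGVHD in the 72 hours before consent, and 5.3.2.2 lets them continue. Their questionnaires come after consent. For these subjects the last pre-dose score follows some days of treatment. It remains usable as a covariate but should be described accurately.

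**What to change.** Keep the step-5 Lee responder test, the descriptive means and the plots. Add to SAP Section 4:

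- A mixed model for repeated measures on change from baseline, for the Lee total score and the SF-36 scores. Terms: arm, visit, arm-by-visit, baseline score and baseline-by-visit.
- The adjusted arm difference with 95% CI at Weeks 25 and 49, labelled supportive for Lee and exploratory for SF-36.
- A statement of which SF-36 scores are analysed, reconciling the protocol's summary scores with the SAP's subscales.
- Baseline defined as the last score before the first dose of study drug, noting that for some subjects it follows the start of corticosteroids.
- Inclusion of questionnaires completed after cGVHD progression, mapped to visits by stated windows.
- A table by arm and visit of the number contributing, deaths and missing forms, with the missing-at-random assumption stated and a note that the model does not resolve death.

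The cost is SAP wording and standard programming. No new data and no alpha are needed. SAP 1.7.1 describes the sponsor as blinded, so the model can be specified before unblinding.

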5. SAFETY

Safety data will be summarized by arm for the safety population and where appropriate for the pediatric subgroup. Table 3 summarizes the planned safety analyses. Adverse events (AEs) will be coded in accordance with the Medical Dictionary for Regulatory Activities (MedDRA) version 22.1. Severity of AEs will be graded by the investigator according to the NCI-CTCAE v4.03 for hematologic and non-hematological AEs.

The primary analysis will use the ibrutinib/placebo treatment-emergent period, which will include all reported AEs satisfying any of the following criteria:

- Those events that occurred or worsened after the first dose of ibrutinib/placebo, through the treatment phase, and within 30 days following the last dose of ibrutinib/placebo or initiation of subsequent cGVHD systemic therapy, whichever occurred first.
- Events with a missing onset date with a resolution date during the ibrutinib/placebo treatment phase; or
- Events that were considered study drug-related regardless of the start date of the event.

For completeness, an additional analysis will be performed to assess AEs that occurred while the patient was being treated with either component of the study treatment (ibrutinib/placebo and/or prednisone; hereinafter referred to as study treatment AEs) and which will include all reported AEs satisfying any of the following criteria:

- Those events that occurred or worsened after the first dose of ibrutinib/placebo or prednisone, through the treatment phase, and within 30 days following the last dose of ibrutinib/placebo or prednisone, or initiation of subsequent cGVHD systemic therapy, whichever occurred first.
- Events with a missing onset date with a resolution date during the ibrutinib/placebo or prednisone treatment phase; or
- Events that were considered related to either ibrutinib/placebo or prednisone regardless of the start date of the event.

Summaries of treatment emergent AEs (TEAEs) and study treatment AEs will be provided, unless otherwise specified.

All laboratory values will be converted to and reported as international standard (SI) units. In general, only data from the central laboratory will be summarized and analyzed. All gradable laboratory parameters will be graded using the NCI CTCAE v4.03. Unless otherwise specified, only baseline and post-baseline values collected during the ibrutinib/placebo treatment-emergent period will be included in the safety analysis. Additionally, summary of hematologic toxicity will be provided.

Table 3: Summary of Safety Analyses

Assessment Type	Definition	Methods
Study treatment (ibrutinib/placebo and/or prednisone) adverse events	Study treatment AEs, serious study treatment AEs, Grade 3 or higher study treatment AEs, study treatment AEs related to prednisone, study treatment AEs leading to prednisone treatment discontinuation. Study treatment AEs resulted in death Predefined corticosteroid-associated AEs will be summarized	Descriptive summary statistics and/or listings
Ibrutinib/placebo TEAEs	TEAEs, TE SAEs, Grade 3 or worse TEAEs, Related TEAEs TEAEs leading to treatment discontinuation, TEAEs leading to dose reduction. TEAEs related to corticosteroids, TEAEs leading to corticosteroid treatment discontinuation. TEAEs resulting in death Protocol-defined events of special interest (major hemorrhage) and other safety observations Predefined corticosteroid-associated AEs will be summarized	Descriptive summary statistics and/or listings
Central Laboratory results collected during the ibrutinib/placebo TEAE period	Worst post-baseline toxicity grade for selected CTCAE gradable hematology and chemistry laboratory measurements. Liver function abnormalities.	Descriptive summary statistics and/or listings
Vital Signs collected during the ibrutinib/placebo TEAE period	Blood pressure, heart rate	Descriptive summary statistics and/or listings

AE: adverse event; TEAE= treatment-emergent adverse events as defined in Section 5; SAE= serious adverse event; CTCAE= Common Terminology Criteria for Adverse Events.

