#### **7.1.1.5. Adverse Events**

The accepted regulatory definition for an AE is provided in [Section 11.1](#). The occurrence of an AE from the time the ICF is signed until first dose should be recorded under medical history in the eCRF form. All medical occurrences after the first dose of ibrutinib/placebo or prednisone until 30 days after the last dose of ibrutinib/placebo or prednisone, start of new medication for cGVHD or start of a new therapy for progression of the underlying malignancy that meet the AE definition must be recorded as AEs in the eCRF. If the subject rolls over into a follow-up study, AE collection will stop after the last dose is given as part of that study. Laboratory abnormalities designated clinically significant by the investigator will also be documented as AEs. Assessment for corticosteroid-related AEs, in particular ([Appendix Q](#)), should be performed. Additional important requirements for AE and SAE reporting are explained in [Section 11.4](#).

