### **Adverse Events**

The verbatim terms used in the eCRF by investigators to identify AEs will be coded using the Medical Dictionary for Regulatory Activities (MedDRA).

Treatment-emergent period is defined as the period of time from the first dose of study treatment, until the earlier of:

- Thirty days following the last dose of ibrutinib/placebo or prednisone whichever occurs later
- OR

- The start date of a new therapy for cGVHD or for the progression of the underlying malignancy.

The TEAEs are those events that:

- Are not present prior to the treatment-emergent period and occur during the treatment-emergent period,
- Are considered related to study drug by the investigator regardless of the start dates of the events, or
- Are present prior to the treatment-emergent period but worsen in severity during the treatment-emergent period or are subsequently considered related to study drug by the investigator.

All treatment-emergent AEs will be summarized. For each AE, the number and percentage of subjects who experience at least one occurrence of the given event will be summarized. The number and percent of subjects with TEAEs will be summarized according to intensity (CTCAE, v4.03) and drug relationship, as well as categorized by system organ class and preferred term. Summaries and listings may be provided, as appropriate, for those subjects who die, who discontinue treatment due to an AE, or who experience a severe or a SAE.

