### 11.4.2. Adverse Event Reporting Period

All AEs whether serious or non-serious, will be documented from the time signed and dated ICF is obtained until 30 days following the last dose of study drug (ibrutinib/placebo or prednisone) or the start date of a new therapy for cGVHD. The occurrence of AE at the time the ICF is signed until first dose should be recorded under medical history in the eCRF form. All medical occurrences after the first dose of study drug until 30 days after the last dose of study drug that meet the AE definition must be recorded as AEs in the eCRF. SAEs will be reported to the Sponsor Drug Safety via an SAE reporting form and will be recorded in the eCRF from the time of ICF signing. Serious adverse events reported after 30 days following the last dose of study drug should also be reported if considered related to study drug. Resolution information after 30 days should be provided.

Progression of cGVHD should NOT be reported as an event term, but instead symptoms/clinical signs of disease progression may be reported (see [Section 11.1.1](#)).

All AEs, regardless of seriousness, severity, or presumed relationship to study drug, must be recorded using medical terminology in the source document. All records will need to capture the details of the duration and the severity of each episode, the action taken with respect to the study drug, investigator's evaluation of its relationship to the study drug, and the event outcome. Whenever possible, diagnoses should be given when signs and symptoms are due to a common etiology (eg, cough, runny nose, sneezing, sore throat, and head congestion should be reported as "upper respiratory infection"). Investigators must record in the CRF their opinion concerning the relationship of the AE to study therapy. All measures required for AE management must be recorded in the source document and reported according to Sponsor instructions.

All deaths should be reported with the primary cause of death as the AE term, as death is typically the outcome of the event, not the event itself. Autopsy and postmortem reports must be forwarded to the Sponsor, or designee, as outlined above, if allowed per local regulatory guidelines.

If a death occurs within 30 days after the last dose of study drug, the death must be reported to the Sponsor as a SAE.

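### Both adverse-event windows in SAP Section 5 drop the protocol's cut-off at the start of relapse therapy without declaring it, and the protocol's own recording rules disagree on the same point

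*SAP*

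**What the plan says.** **Analysis windows.** Protocol 10.5 (Adverse Events) takes the earlier of two limits. One is "Thirty days following the last dose of ibrutinib/placebo or prednisone whichever occurs later". The other is "The start date of a new therapy for cGVHD or for the progression of the underlying malignancy". SAP Section 5 defines two windows. The primary one closes "within 30 days following the last dose of ibrutinib/placebo or initiation of subsequent cGVHD systemic therapy, whichever occurred first". The additional study-treatment window closes "within 30 days following the last dose of ibrutinib/placebo or prednisone, or initiation of subsequent cGVHD systemic therapy, whichever occurred first". Neither mentions treatment of the underlying malignancy.

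**Recording rules.** Protocol 7.1.1.5 lists among its stops "start of new medication for cGVHD or start of a new therapy for progression of the underlying malignancy". Protocol 11.4.2 has no malignancy stop. Its first sentence runs "until 30 days following the last dose of study drug (ibrutinib/placebo or prednisone) or the start date of a new therapy for cGVHD". Its third sentence drops even the cGVHD stop: "All medical occurrences after the first dose of study drug until 30 days after the last dose of study drug" are to be recorded if they meet the definition of an adverse event.

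**Precedence.** SAP Section 1 says that the SAP overrides the protocol, and SAP Section 1.2 sends the reader to Section 6 for departures. Section 6 has two entries: the corticosteroid and immunosuppressant withdrawal endpoints, and the move of Karnofsky scores to exploratory efficacy. The safety window is not there.

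**The concern.** Protocol 9.2 stops ibrutinib/placebo at relapse, and treatment of the malignancy may follow within days. Cytopenias and infections are listed ibrutinib risks (protocol 1.2.4) and are also plausible toxicities of relapse therapy. Under protocol 10.5 an unrelated event that begins after relapse therapy starts is not treatment-emergent. Under the SAP it is, if it was reported and falls within 30 days of the last ibrutinib/placebo dose.

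The tables exposed are the all-causality ones in SAP Table 3: TEAEs, serious TEAEs, Grade 3 or higher TEAEs and TEAEs resulting in death. The laboratory tables inherit the window, because SAP Section 5 restricts them to the ibrutinib/placebo treatment-emergent period and reports the worst post-baseline grade. The End-of-Treatment visit (protocol 8.2.3) includes hematology about 30 days after the last dose, with a 7-day allowance. It is brought forward for new cGVHD treatment but not for malignancy therapy. A sample from day 23 to day 30 can therefore show the marrow effect of another regimen.

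The omission does not look deliberate. The same SAP treats relapse as a competing or ending event for both withdrawal endpoints, the Lee score and duration of response.

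**Working it through.** The plan gives no figure to reproduce here, so the check is a comparison of the rules followed by a bound.

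**Step 1: one subject under each rule.** Assumed days: last ibrutinib/placebo L = 100, relapse therapy M = 105, last prednisone P = 160, no new cGVHD therapy.

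| Rule | Formula | Closes on day | Unrelated, non-serious event on day 115 |
|---|---|---|---|
| Protocol 7.1.1.5, recording | min(max(L, P) + 30, M), reading its stops as earliest-first | 105 | not recorded |
| Protocol 11.4.2, recording | max(L, P) + 30 | 190 | recorded |
| Protocol 10.5, treatment-emergent | min(max(L, P) + 30, M) | 105 | not a TEAE |
| SAP 5, primary | L + 30 | 130 | TEAE if reported |
| SAP 5, study treatment, later drug | max(L, P) + 30 | 190 | counted if reported |
| SAP 5, study treatment, literal reading | min(L, P) + 30 | 130 | counted if reported |

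Two readings are my assumptions. Protocol 7.1.1.5 does not say which of its stops governs. The SAP's second window does not make clear whether its 30 days run from the earlier or the later of the two drugs; protocol 10.5 says the later. With the 10.5 cut-off restored, both SAP windows would close on day 105 for this subject.

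**Step 2: a ceiling on the effect.** Inputs: 193 subjects enrolled (SAP 1.1). Background 73.8% with a Grade 3 or higher event and 52.4% with a serious event (protocol 1.2.3.3, 42 subjects in the Phase 1b/2 cGVHD study). The share r who relapse and start therapy inside the window is not in the documents; I assume 5% to 15%.

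Subjects: 193 × 0.05 = 9.7 and 193 × 0.15 = 29.0, so about 10 to 29.

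Suppose that every such subject then has a new recorded event, and that relapsed subjects carry the same background risk as the rest. The rise in the proportion with at least one event is at most r × (1 − background):

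- Grade 3 or higher: 0.05 × 0.262 = 1.3 points; 0.15 × 0.262 = 3.9 points.
- Serious: 0.05 × 0.476 = 2.4 points; 0.15 × 0.476 = 7.1 points.

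**Step 3: between arms.** If r is equal in both arms and relapsed subjects are handled alike, the shift is the same in both and the difference is unaffected. If r were 5% in one arm and 15% in the other, the spurious Grade 3 or higher difference would be at most (0.15 − 0.05) × 0.262 = 2.6 points under the same assumptions.

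**The case against.** The case for leaving the plan alone has weight.

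- The longer window is inclusive: it discards no reported event. No formal safety testing is planned (protocol 10.5), and the SAP describes reported events without person-time denominators.
- Events judged related to study drug count whatever their start date, and related TEAEs have their own table. Investigators can attribute relapse-therapy toxicity elsewhere. The cut-off therefore matters only for events judged unrelated.
- Ibrutinib/placebo stops at relapse, which limits the overlap in the primary window to 30 days. The study-treatment window can run longer if prednisone continues.
- Protocol 7.1.1.5 refers sites to 11.4, which requires any death within 30 days of the last dose to be reported as an SAE and related SAEs to be reported even after that. Under-recording is therefore mainly of non-serious, unrelated events.

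All of this stands, and it limits the effect. It does not justify an undeclared departure from 10.5, and the all-causality and laboratory tables still change.

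A reader might go further and infer that some sites recorded these events while others did not. The documents do not show which section any site followed, and protocol 7.1.1.5 and 11.4.2 may have been reconciled in the CRF completion guidelines. A reader might also infer that whether a death is reported depends on the section followed; the 30-day death rule excludes that. What can change is whether a reported fatal event is tabulated as treatment-emergent.

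**Conclusion.** The concern holds as a conflict in the text with a limited analytic consequence. Both SAP windows omit a cut-off that protocol 10.5 contains, the omission is undeclared, and two protocol sections give different recording stops. Followed as written, the SAP can tabulate toxicity of relapse therapy as ibrutinib/placebo TEAEs and worst laboratory grades, while some mainly non-serious, unrelated events can go unrecorded.

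The size is unknown. The 1.3 to 3.9 points for Grade 3 or higher events is a ceiling. It rests on an assumed relapse share, on every such subject starting therapy inside the window and having a new recorded event, and on a background rate from subjects who had already failed steroids. The 10 to 29 subjects should not be read as a count of those affected. Nor do the documents support a claim that the between-arm comparison is biased: that needs relapse or its treatment to differ by arm, and they give no data on either.

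**What to change.** 1. In SAP Section 5, add to both windows that they also close when therapy for progression of the underlying malignancy starts, as in protocol 10.5. The laboratory tables then follow the primary window. State whether the 30 days in the study-treatment window run from the earlier or the later drug.
2. List by arm, separately, the events between that start and day 30 (or the later end of the study-treatment window), so that nothing reported is lost from view.
3. Record in SAP Section 6 any departure from 10.5 that remains, including the primary window's use of ibrutinib/placebo alone for the 30-day limit. If the sponsor prefers the longer window, it should be declared there.
4. Confirm that the start date of malignancy therapy is in the database. The stop rules in 7.1.1.5 and 10.5 presuppose it, but concomitant-medication recording can end at that same point (protocol 6 and 7.1.1.4), and long-term follow-up (8.3.2) names only survival and alternative cGVHD therapy.
5. Reconcile 7.1.1.5 with 11.4.2, and the first and third sentences of 11.4.2 with each other, for subjects still under adverse-event recording. With 193 subjects already enrolled, an amendment cannot be assumed to recover events that went unrecorded, and it needs ethics approval.

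The cost on the SAP side is a clause in each window, one listing, an entry in Section 6 and a data check.
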